1. SCOPE

This study protocol specifies objective, design and methods for the assessment of assessment of nutrient profile, nutritional status, development and severity of children with autistic spectrum disorder in comparison with typically developing children in Addis Ababa, Ethiopia

2 DEFINITION OF TERMS

- a) AL-cup: the type of glass and non-glass cups used exclusively for laboratory purposes.For instance in the analysis of fat.
- **b) Desiccator:** a glass container or other apparatus holding a drying agent for removing moisture from sample and protecting them from surrounding moisture.
- c) Digestion: heating of a sample in extreme temperatures using various reagents that corresponds to the type of analysis.
- **d) PH**: measure of level of acidity and Alkalinity (base) on a scale of 1 to 14. Lower PH indicating higher acidity while higher PH indicates the alkalinity of a substance.
- e) Cruisable: ceramic bowl container used in the analysis of samples that involve direct heat exposer or of stored in an oven with elevated temperature
- f) Titration: a slow addition of a solution of a known concentration (titrant) to a known solution of unknown concentration until the reaction reaches neutralizations, which is often indicated by a change of color.
- g) Muffle furnace: a type of jacketed enclosure that is used to heat a material to a significantly high temperature while keeping it contained and fully isolated from external contaminants.
- h) Spectrophotometry: a method of measuring how much a chemical substance absorbs light by measuring the intensity of light as a beam of light passes through sample solution.

- i) Colorimetery: a method of determining the concentration of a chemical agent with the aid of a color reagent and its light absorption.
- **j)** Thimble: apparatus of fat analysis equipment (soxhlet extractor) that is usually made of thick filter paper which retains the solid to be extracted.

2. OBJECTIVES

2.1. General objectives

The general objective of this study is to assess the nutritional status, nutrient profile, ASD severity, and development of children diagnosed with ASD as compared to typically developing controls in Addis Ababa, Ethiopia.

2.2. Specific objectives

The specific objectives of this study are to:-

- 1. Evaluate the nutrient profile of diets using proximate analysis.
- 2. Determine the nutritional status (i.e. stunting, wasting, underweight and overweight)of children diagnosed using anthropometric measurements.
- 3. Assess the dietary diversity score (DDS) of children using food frequencyquestioners (FFQ).
- 4. Examine the urine samples of children to identify the urine iodine (UI) level.
- 5. Assess the parents and caregivers perceptions about the Eating behaviour of ASD children using questioner.
- 6. Evaluate the ASD severity level and developmental growth of children with ASD in correlation to UI level.

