4. SUBJECTS

Selection of 26 children with Autistic Spectrum Disorder (ASD) (case group) and the corresponding 26 typically developing children (control group), 52 children in total, shall be made on the basis of:

4.1.Inclusion criteria

- a) Children that are already diagnosed with ASD for the "case" group,
- b) Children fulfilling the matching criteria to the case group (i.e. age and sex) for the control group.

4.2.Exclusion criteria

- a) Use of special supplements,
- b) Use of heavy medication,
- c) Children with critical chronic disease such as cancer, HIV AIDs.

4.3.Test conditions

The subjects shall:

- a) Be of school age;
- b) Legal guardians of the child need to Sign a consent form for the willingness of his/her participation;
- c) Give the necessary information and specimen agreed upon in the given consent forms.

The analysis shall:

a) Be conducted by

- The researcher as per guidelines and procedures described for all nutritional analysis.
- Registered nurse for urine sample collection
- Registered physician for CARS diagnosis.
- b) Have no risk involved since it doesn't involve any penetration to the human muscle
- c) Be done with the willingness of the participant and their legal guardians (he/she can stop the participation anytime)

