5.5. CARS diagnosis

CARS is scale that is frequently used in the diagnosis of ASD in children. It consists of 15 items that cover different symptoms of ASD, and provides a reliable comparison of an affected child's behaviors and skills against the expected developmental growth of a healthy child. The diagnosis will be conducted by a physician by combining parent reports (direct question and answer) and direct observations of children made by the clinician.

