6.3. Statistical analysis plan

Given the variability of the type of data generated from each assessment, data analysis and interpretation shall be done in the respective the nature of each data.

Anthropometric measurement data shall be analyzed using corresponding index of Weight for height, height for age, weight for age and MUAC for age and interpreted using international standards. ENA 2020 shall be used to record the measurements and convert to respective Z-scores.

The Data generated from CARS diagnosis will be on a scale from one (normal behavior) to four (severely abnormal behavior) for each category of questions. The scores between 30 and 37 indicate mild to moderate ASD, while scores between 38 and 60 indicate severe ASD. These results shall be analyzed by SPSS version 26 for descriptive statistics and correlations

In case of urine iodine analysis, the decrease in yellow color over a fixed period is measured by a colorimeter with an appropriate filter or with a spectrophotometer and plotted against a standard

curve constructed with known amounts of iodine. The resulting reading of iodine content shall then be compared among case and control groups of the study. SPSS version 26 shall be used to for descriptive statistics, significant difference and correlations

The data generated from proximate analysis of food samples shall be recorded for each analysis and calculated for average. The final figure represents the amount of nutrient present per 100 gm. thus amounts consumed by children. This data shall then be compared among case and control groups of the study. SPSS version 26 will also be used for descriptive statistics, significant difference and correlations

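### The severity-iodine correlation in objective 6 is planned within the cases with no adjustment for age, and matching controls on age does not supply one

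*Combined protocol and SAP*

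**What the plan says.** Section 2.2, item 6, sets the aim: "Evaluate the ASD severity level and developmental growth of children with ASD in correlation to UI level". It concerns children with ASD only, so the controls do not enter it.

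Section 6.3 gives the analysis. For CARS: "These results shall be analyzed by SPSS version 26 for descriptive statistics and correlations". For urine iodine: "SPSS version 26 shall be used to for descriptive statistics, significant difference and correlations". Neither sentence names a type of correlation, a covariate, a regression or an age stratum.

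Age appears in three other places:

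- Section 4.1 uses it to select controls: "Children fulfilling the matching criteria to the case group (i.e. age and sex) for the control group".
- Section 4.3 requires subjects to "Be of school age", with no limits in years.
- Section 6.3 uses it in the anthropometric indices: "Weight for height, height for age, weight for age and MUAC for age".

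Section 5.5 also bears on the point. It describes CARS as a comparison of the child's "behaviors and skills against the expected developmental growth of a healthy child".

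**The concern.** Matching makes the two groups alike in age. Objective 6 compares one case with another, and choosing controls of the same ages leaves the age spread among the 26 cases exactly as it was. A reader who sees age matching in section 4.1 could wrongly take age to be dealt with here as well.

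If older and younger cases differ systematically in both CARS score and urine iodine, an unadjusted correlation mixes that age pattern with any relation between severity and iodine. Age effects in the same direction can produce an apparent relation, and effects in opposite directions can hide a real one. No other objective links iodine to ASD severity, so nothing else in the plan would expose the problem.

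**Working it through.** The plan states no alpha, power, effect size or sample-size calculation, so it has no figure of its own to reproduce.

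**Inputs.** From the documents: n = 26 cases (section 4). Assumed: two-sided 5% test, normally distributed CARS total and iodine, and a range of correlations of age with each, because the documents give none.

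**Step 1, threshold.** Critical |r| = t / √(df + t²). Simple correlation: df = 24, t = 2.064, so 2.064 / √(24 + 4.260) = 0.388. Partial correlation given age: df = 23, t = 2.069, so 2.069 / √(23 + 4.279) = 0.396.

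**Step 2, false positives.** With no relation at a given age, the expected simple correlation is r(age, CARS) × r(age, iodine). Rejection rates are simulated, with 40,000 data sets per row:

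| age–CARS / age–iodine | expected simple r | unadjusted | age-adjusted |
|---|---|---|---|
| 0.5 / 0 | 0 | 5.1% | 5.1% |
| 0.2 / 0.2 | 0.04 | 5.4% | 5.0% |
| 0.3 / 0.3 | 0.09 | 7.4% | 5.0% |
| 0.4 / 0.4 | 0.16 | 12.0% | 5.0% |
| 0.5 / 0.5 | 0.25 | 23.4% | 5.1% |

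A separate simulation of 20,000 data sets gives 7.2%, 12.5% and 23.9% unadjusted for the last three rows. With unequal links the unadjusted rate is 5.3% at 0.1 / 0.3, 5.8% at 0.1 / 0.5 and 6.5% at 0.2 / 0.4.

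**Step 3, masking.** Take a true partial correlation of 0.5 and age effects of +a on one measure and −a on the other. The simple correlation is −a² + 0.5 × (1 − a²):

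| a | simple r | power, unadjusted | power, age-adjusted |
|---|---|---|---|
| 0 | 0.50 | 77% | 75% |
| 0.1 | −0.01 + 0.495 = 0.485 | 74% | 75% |
| 0.2 | −0.04 + 0.48 = 0.44 | 64% | 75% |
| 0.3 | −0.09 + 0.455 = 0.365 | 46% | 75% |
| 0.4 | −0.16 + 0.42 = 0.26 | 25% | 75% |

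**Step 4, price of adjusting.** Detectable r at 80% power = tanh(2.8016 / √(n − 3 − k)), with k covariates:

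- k = 0: tanh(2.8016 / √23) = 0.526
- k = 1 (age): tanh(2.8016 / √22) = 0.535
- k = 2 (age and sex): tanh(2.8016 / √21) = 0.545

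**The case against.** The strongest reply is that the bias is hypothetical. It needs age to be related to both measures, and the documents report neither relation. Section 5.5 describes CARS as judged against expected development, which may weaken its link with age. If that link is only 0.1, the false-positive rate is 5.8% even when age and iodine correlate at 0.5. For iodine, the net direction is also unclear: larger intake would raise the concentration and larger urine volume would lower it. All this stands, and it limits how strongly the point can be put. It does not remove the point, because a rating made with development in mind is not an adjustment in the analysis, and section 6.3 gives no age norms for CARS.

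Four stronger readings are tempting, and the documents do not support them:

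- **That the plan chose an unadjusted correlation.** Section 6.3 says only correlations. The type is left open, so the defect is that no adjustment is specified.
- **That age is likely to account for any finding.** For age alone to bring the expected r to the 0.388 threshold, it would have to correlate at about √0.388 = 0.62 with both measures. Nothing in the documents points to links that strong.
- **That the ages of the cases are unrestricted.** School age is a restriction, though without stated limits. A narrow achieved range would shrink the problem.
- **That every child-level correlation needs the same adjustment.** The for-age indices in section 6.3 already account for age.

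**Conclusion.** The point holds as a conditional one. Objective 6 is a within-case correlation, no age adjustment is planned, and the matching does not provide one. Whether this distorts the result depends on two correlations that the documents do not give.

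The false-positive problem is negligible if either link is near zero, small when both are 0.3 or less (about 7% against 5%), and material from about 0.4 upwards. Loss of power under opposite age effects appears sooner, with about 11 percentage points lost at 0.2 and 29 at 0.3, but those figures also assume a true partial correlation of 0.5. All figures assume normal data and a continuous CARS total, and they concern age only; no corresponding calculation supports a distortion by sex.

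The case for acting rests on the balance of costs. The age data are already needed for matching and for the for-age indices, and adjusting for age costs almost nothing.

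**What to change.** In section 6.3, state that the severity part of objective 6 is a partial correlation of CARS total score with urine iodine in the cases, adjusted for age as recorded. Use a rank-based version if iodine is skewed. Report the estimate with its 95% CI and show the unadjusted correlation alongside. Adding sex is optional. Do not extend the age adjustment to indices already standardised for age.

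No new data are needed. The cost is one degree of freedom for age, with the correlation detectable at 80% power moving from 0.53 to about 0.54, or 0.55 if sex is added. If age turns out to have no effect, power for a true correlation of 0.5 falls slightly, from about 77% to 75%.

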3. MATERIALS

- a) Weight scale
- b) Height board measurement
- c) Middle Upper Arm Circumference tape
- d) CARS standard version rating booklet

- e) Food collection Bag
- f) Urine collection cup
- g) Proximate and urine analysis equipments and chemicals (hexane, H₂SO₄, Ethanol, digester, soxhlet extractor, etc.)

4. SUBJECTS

Selection of 26 children with Autistic Spectrum Disorder (ASD) (case group) and the corresponding 26 typically developing children (control group), 52 children in total, shall be made on the basis of:

4.1.Inclusion criteria

- a) Children that are already diagnosed with ASD for the "case" group,
- b) Children fulfilling the matching criteria to the case group (i.e. age and sex) for the control group.

4.2.Exclusion criteria

- a) Use of special supplements,
- b) Use of heavy medication,
- c) Children with critical chronic disease such as cancer, HIV AIDs.

4.3.Test conditions

The subjects shall:

- a) Be of school age;
- b) Legal guardians of the child need to Sign a consent form for the willingness of his/her participation;
- c) Give the necessary information and specimen agreed upon in the given consent forms.

The analysis shall:

a) Be conducted by

- The researcher as per guidelines and procedures described for all nutritional analysis.
- Registered nurse for urine sample collection
- Registered physician for CARS diagnosis.
- b) Have no risk involved since it doesn't involve any penetration to the human muscle
- c) Be done with the willingness of the participant and their legal guardians (he/she can stop the participation anytime)

5. PROCEDURE

5.1. Height

A child height board will be used to measure height of the children. The children will be measured with minimal clothing and no shoes and socks must be worn. The feet must be together, arms to the side, legs straight and shoulders relaxed, the head must be in the Frankfort horizontal plane (looking straight ahead). An average of 3 readings will be taken and read to the nearest 0.1 cm.

5.2. MUAC (Middle Upper Arm Circumference)

MUAC is the circumference of the left upper arm and is measured at the mid-point between the tips of the shoulder and elbow using a MUAC tape. To measure:

Bend the left arm, find and mark with a pen the olecranon process and acromium.

- Mark the mid-point between these two marks.
- With the arm hanging straight down, wrap a MUAC tape around the arm at the midpoint mark.
- Measure to the nearest 1 mm

5.3. Weight

The children will be measured using an electronic weight scale with minimal clothing and no shoes and socks must be worn. The scale will be placed on a hard, flat (level) surface up on measurement and scale reading

5.4. Urine collection

60 ml. urine samples will be collected from each child by a trained clinical practitioner (nurses), at the child's period of urinary stimulation, using sample collection cups.

5.5. CARS diagnosis

CARS is scale that is frequently used in the diagnosis of ASD in children. It consists of 15 items that cover different symptoms of ASD, and provides a reliable comparison of an affected child's behaviors and skills against the expected developmental growth of a healthy child. The diagnosis will be conducted by a physician by combining parent reports (direct question and answer) and direct observations of children made by the clinician.

5.6. Food sample collection

50gm sample of food will be collected in sample collection bags from each meal consumed throughout the day by the researcher and legal guardians.

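### Section 5.6 samples food by the undefined unit of a meal and makes no provision for between-meal foods or drinks, yet the result is read as the nutrient profile of diets and as intake

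*Combined protocol and SAP*

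**What the plan says.** Section 5.6 is the only rule for collecting food: "50gm sample of food will be collected in sample collection bags from each meal consumed throughout the day", with the researcher and guardians as collectors. The word for the sampling unit is not defined. Snacks and drinks are neither included nor excluded there or anywhere else. For diet, the materials list in section 3 names only a bag for food; the one cup on the list is for urine.

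The use made of these samples is wider than the rule. Objective 1 in section 2.2 is "Evaluate the nutrient profile of diets using proximate analysis". Section 6.3 then states "The data generated from proximate analysis of food samples shall be recorded for each analysis and calculated for average", with no weights given, and continues "The final figure represents the amount of nutrient present per 100 gm. thus amounts consumed by children". The group comparison follows: "This data shall then be compared among case and control groups of the study". Section 4 sets 26 cases and 26 controls.

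The other dietary instrument is the food frequency questionnaire in objective 3. It is tied to a dietary diversity score. Section 6.3 gives no analysis for it and no link to the proximate results.

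**The concern.** What is claimed and what is sampled do not match. The claim concerns the diet and the amounts eaten; the written rule provides for food from meals. Bread, biscuits, fruit, milk, juice or sweetened tea taken outside a meal have no stated route into the proximate data, and a bag does not suit a drink. The questionnaire does not close the gap, because a food recorded there adds to a diversity score and not to protein, fat, fibre or ash.

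The comparison between groups is what is at stake. Two groups with similar meals could have different diets, and the planned comparison would show them as alike. Because guardians collect samples alongside the researcher, an undefined unit may also be applied differently from one family to the next. Food that was never collected cannot be recovered in the analysis, so the rule has to be settled before collection starts.

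**Working it through.** The plan gives no figure to reproduce: it states no between-meal share, no amounts eaten and no nutrient densities. The values below are assumptions, used only to show how the gap works.

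**Formula.** Let M be the nutrient density of meals, S that of between-meal items (both in g per 100 g), and f the share of food mass taken between meals. Then

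whole-diet density = (1 − f) × M + f × S.

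Meals-only sampling returns M. If M is the same in both groups, the difference that goes unseen is

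f₁ × (S₁ − M) − f₀ × (S₀ − M),

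with 1 for cases and 0 for controls. If S is also common, this reduces to (f₁ − f₀) × (S − M).

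**Numbers for fat, with M = 5 in both groups.** Meals-only sampling shows a difference of 0 in every row.

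| f cases | f controls | S cases | S controls | Diet, cases | Diet, controls | Unseen difference |
|---|---|---|---|---|---|---|
| 0.30 | 0.15 | 20 | 20 | 9.5 | 7.25 | 2.25 |
| 0.30 | 0.15 | 10 | 10 | 6.5 | 5.75 | 0.75 |
| 0.30 | 0.15 | 30 | 30 | 12.5 | 8.75 | 3.75 |
| 0.20 | 0.10 | 20 | 20 | 8.0 | 6.5 | 1.5 |
| 0.40 | 0.10 | 20 | 20 | 11.0 | 6.5 | 4.5 |
| 0.20 | 0.20 | 20 | 10 | 8.0 | 6.0 | 2.0 |
| 0.10 | 0.10 | 20 | 20 | 6.5 | 6.5 | 0 |
| 0.30 | 0.15 | 5 | 5 | 5.0 | 5.0 | 0 |

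First row in full: cases 0.70 × 5 + 0.30 × 20 = 3.5 + 6 = 9.5; controls 0.85 × 5 + 0.15 × 20 = 4.25 + 3 = 7.25; difference 2.25.

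The last two rows show when nothing is missed: between-meal share and composition are the same in both groups, or between-meal items match meals for that nutrient. Unequal shares alone are not enough to create a gap. The sixth row shows that equal shares with different composition can create one. Exchanging the groups' values reverses the sign.

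**Does adding a snack sample suffice?** Take the average in section 6.3 as a simple one, since no weights are stated, and assume three meals at 5 plus one pooled between-meal sample:

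- S = 20: (5 + 5 + 5 + 20) / 4 = 8.75 in both groups, difference 0.
- S = 10: 25 / 4 = 6.25 in both groups, difference 0.
- S = 30: 45 / 4 = 11.25 in both groups, difference 0.

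The 2.25 in the first row comes from the mass shares, and a simple average never uses them. Weighting by mass eaten gives 9.5 and 7.25 again and recovers the 2.25. The remedy therefore needs recorded amounts as well as extra samples.

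**The case against.** The strongest reply is that the text is silent on snacks and does not exclude them. The rule speaks of what is consumed across the day and does not restrict itself to main meals, so a field worker could apply it to every eating occasion. A food that a child eats in place of the family dish is, on a natural reading, that child's meal and would be sampled. This stands: a reader might infer that snacks and drinks are excluded by design, and the documents do not say so. What they show is a rule that provides for meals and leaves the unit undefined.

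A reader might also infer that a real case-control difference is being missed. The documents do not support that either. They hold no data on between-meal intake in either group. Objective 5 plans to assess caregivers' perceptions of eating behaviour in children with ASD and says nothing about eating between meals. The illustration sets meals equal in both groups, so its meals-only result is 0 by construction; it shows a mechanism and does not estimate a bias.

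The reply does not remove the mismatch. On the literal reading, the data support a statement about sampled meals, while the plan draws one about diets and intake. On the generous reading, the rule still needs to be written down so that it is applied alike to cases and controls.

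**Conclusion.** The concern holds as a gap between what the sampling rule provides for and what the plan concludes. Followed literally, section 5.6 cannot show a group difference that arises from the share or composition of between-meal foods and drinks, and no other part of the plan measures their nutrients. Whether such a difference exists is unknown from the documents.

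The unseen difference in fat runs from 0 to 4.5 g per 100 g across the assumed values shown, and it depends entirely on them. It cannot be expressed in standard deviations, because the plan gives none.

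A related weakness bears on the remedy: a fixed 50 g from each meal, averaged without the weight of food eaten, does not give amounts consumed even for meals. The point should be settled before food collection begins.

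**What to change.** **Preferred.** In section 5.6, state that every eating and drinking occasion on the sampled day, except plain water, is sampled, with the same instruction for cases and controls and a suitable container for drinks. Record the amount eaten or drunk at each occasion, meals included. Between-meal items may be pooled for each child if the pool is made up in proportion to the amounts eaten. In section 6.3, replace the simple average with one weighted by amount eaten.

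**Cost.** Up to one more set of proximate assays per child per sampling day, plus the work of recording amounts. Section 6.1 lists five assays (moisture, protein, ash, fat, fibre), so 52 × 5 = 260 extra assays per sampling day, or 52 × 6 = 312 determinations if the duplicate fibre portions are counted separately. If drinks are pooled apart from solids, these double to 520 and 624.

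**If that is not feasible.** Reword objective 1 and the section 6.3 conclusion to 'nutrient density of sampled meals', and delete the clause in section 6.3 that turns the per-100 g figure into intake. This costs nothing.
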